7.2.4 Early Discontinuation Visit

If any subject discontinues the trial early, every effort should be made to complete the Week 24/early discontinuation (ED) evaluations as soon as possible and, whenever possible, prior to starting any new medication or treatment (including rescue treatment). All attempts will be made to not discontinue the subject unless necessary.

If a study subject completes an early discontinuation evaluation for the purpose of receiving rescue treatment, then the medications used as rescue treatment will be detailed in the respective concomitant medications section of the study's EDC system.

8 STATISTICAL METHODS

The statistical considerations summarized in this section outline the plan for data analysis of this study.

Before unmasking, a separate statistical analysis plan (SAP) will be finalized, providing detailed methods for the analyses outlined below.

Any deviations from the planned analyses will be described and justified in the final integrated study report.

Subjects will be randomized by the IRT in a 1:1:1 ratio to 1 of the 3 treatment groups: KVD001 Injection (6 µg/eye or 3 µg/eye) or sham. Allocation to the treatments will be stratified by baseline BCVA (≤ 55 letters vs > 55 letters) and CST at Screening (≤ 450 µm vs > 450 µm) as determined by the study center.

8.1 Study Subjects

8.1.1 Disposition of Subjects

The number and percentage of subjects entering and completing each phase of the study will be presented, stratified by treatment. Reasons for withdrawal post-randomization will also be summarized.

8.1.2 Protocol Deviations

Deviations from the protocol including violations of inclusion/exclusion criteria will be assessed as “minor” or “major” in cooperation with the Sponsor. Major deviations from the protocol that have the potential to impact the efficacy results will lead to the exclusion of a subject from the Per Protocol Set (PPS). Deviations will be defined prior to unmasking.

8.1.3 Analysis Sets

The following analysis sets have been defined for this study:

Full Analysis Set (FAS):	All randomized subjects following the principle of intention-to-treat (ITT). Subjects will be included in the analysis according to the treatment to which they were randomized.
Per-Per Protocol Set (PPS):	All randomized subjects who are compliant with the study protocol, i.e., who do not experience any major protocol deviations. Subjects will be included in the analysis according to the treatment received.
Safety Set (SAF):	All randomized subjects who received at least one dose of study treatment. Subjects will be included in the analysis according to the treatment received.

The primary efficacy analysis will be based on the FAS and a secondary analysis will also be performed based upon the PPS, to assess the sensitivity of the analysis to the choice of analysis set. All safety analyses will be based upon the SAF.

Demographic and baseline characteristics will be evaluated for the FAS and for the PPS. If one or more subject(s) received incorrect trial drug, these data will also be presented for the SAF.

8.2 General Considerations

All statistical tests will be two-sided and will be performed at the 5% level of significance, unless otherwise stated.

Continuous data will be summarized by treatment group using descriptive statistics (number, arithmetic mean, median, standard deviation [SD], minimum, and maximum). Categorical data will be summarized by treatment group using frequency tables (frequencies and percentages).

All analyses will be carried out using SAS Version 9.4 or higher or using other validated software.

Analysis and data conventions:

Definition of baseline

The baseline assessment will be the latest, valid pre-dose assessment available.

Visit windows

Assessments taken outside of protocol allowable windows will be displayed according to the case report form (CRF) assessment recorded by the Investigator.

Unscheduled assessments

Extra assessments (laboratory data or vital signs associated with non-protocol clinical visits or obtained in the course of investigating or managing AEs) will be included in listings, but not summaries. If more than one laboratory value is available for a given visit, the first valid observation will be used in summaries and all observations will be presented in listings. It is noted that invalid laboratory data may not be used (from hemolyzed samples, mishandled samples, quantity not sufficient, or other conditions that would render values invalid).

Unit of Analysis

Ophthalmic safety endpoints will be analyzed for both eyes. Non-ophthalmic safety endpoints will be analyzed with subject as the unit of analysis. For efficacy endpoints, the unit of analysis will be the study eye.

Missing data conventions

In general, data will not be imputed for safety analysis. The primary and secondary efficacy data analyses will be performed on the FAS [REDACTED]. An analysis using observed data only will also be performed in both the FAS and PPS. Additionally, [REDACTED] the FAS for the analysis of the primary and secondary efficacy variables. No exploratory efficacy endpoints or safety endpoints will be imputed. Additional details will be provided in the SAP.

Multiplicity Considerations

No multiplicity adjustments are planned in this exploratory Phase 2a study.

Other considerations

Since central randomization will be used, no testing for treatment by center interaction will be conducted. No multiplicity adjustments are planned.

Any outliers that are detected during the masked review of the data will be investigated. If necessary, queries will be issued to the Investigator, to either correct or confirm the outlier.

8.3 Demographics, Medical History, Baseline Characteristics, and Concomitant Medications

Demographic data, medical history, concomitant diseases, and concomitant medications will be summarized via descriptive statistics, as appropriate, (overall and stratified by treatment group).

Medical history, concomitant medications and AEs will be coded to MedDRA and WHO Drug dictionaries, as appropriate, for the purpose of summarization.

8.4 Treatment Compliance

IVT injection compliance for the study eye will be assessed by determining if subjects received one, two, three or four IVT injections.

8.5 Efficacy Analyses

All efficacy variables will be displayed in subject listings.

8.5.1 Primary Efficacy Analysis

The primary efficacy endpoint is change from baseline in BCVA letter count in the study eye at Week 16. Change from baseline in BCVA letter count will be calculated as Week 16 BCVA letter count minus Day 1 BCVA letter count such that a negative difference indicates a worsening in vision. In addition, treatment comparisons between each dose of the KVD001 Injection and the sham will be calculated as KVD001 Injection minus sham, such that a positive result indicates more letters gained in the KVD001 Injection treatment group.

8.5.1.1 Hypothesis to be Tested

The null hypothesis is that the effects changes from baseline in BCVA letter count at Week 16 for each dose of the KVD001 Injection and the sham procedure on BCVA are identical:

$$H_0: \mu_k - \mu_s = \mu_k - \mu_s = 0,$$

where μ_k is the effect change from baseline in BCVA letter count at Week 16 for each dose of the KVD001 Injection and μ_s is the effect of change from baseline in BCVA letter count at Week 16 for the sham procedure. The alternative hypothesis is that the effect change from baseline in BCVA letter count at Week 16 for each dose of the KVD001 Injection is larger than the effect of change from baseline in BCVA letter count at Week 16 for the sham procedure on BCVA:

$$H_a: \mu_k - \mu_s > 0.$$

8.5.1.2 Statistical Methods

The study eye ETDRS letter scores including changes from baseline will be summarized using continuous descriptive statistics. An analysis of covariance (ANCOVA) model will be used to compare the change from baseline in BCVA letter count at Week 16 between each dose of the KVD001 Injection and the sham. The ANCOVA model will include treatment as a main effect and baseline BCVA letter count as a covariate. Least-squares means (LSMeans) for each treatment group, the LSMean difference between each dose of the KVD001 Injection group and the sham group, the corresponding CIs and the p-values will be presented.

As a sensitivity analysis, treatment group differences for changes from baseline in BCVA letter count will be evaluated using a mixed model repeated measures (MMRM) ANCOVA fitted with treatment group, visit and the treatment by visit interaction as categorical variable terms with baseline BCVA letter score and baseline CST as covariates with contrasts included for each visit. LSMeans and 95% confidence intervals for each treatment group, the LSMeans difference between each dose of the KVD001 Injection and sham, the corresponding confidence intervals, and the p-values will be presented for each visit.

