This SAP is being written with due consideration of the recommendations outlined in the most recent International Conference on Harmonisation (ICH) E9 Guideline entitled Guidance for Industry: Statistical Principles for Clinical Trials and the most recent ICH E3 Guideline, entitled Guidance for Industry: Structure and Content of Clinical Study Reports (CSR).

This SAP describes the data that will be analyzed and the subject characteristics, efficacy, safety and tolerability assessments that will be evaluated. This SAP provides details of the specific statistical methods that will be used. The statistical analysis methods presented in this document will supersede the statistical analysis methods described in the clinical protocol. If additional analyses are required to supplement the planned analyses described in this SAP, they may be completed and will be identified in the CSR.

2. Study Objectives

The primary objective of this study is to evaluate the efficacy of monthly dosing of intravitreal (IVT) injection of KVD001 in subjects with center-involving diabetic macular edema (ciDME) who have had prior anti-vascular endothelial growth factor (anti-VEGF) treatment. The secondary objective is to evaluate the local and systemic safety and tolerability of monthly dosing of KVD001 Injection in subjects with ciDME who have had prior anti-VEGF treatment.

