4.1 Method of Assigning Subjects to Treatment Groups

Screened subjects who sign an informed consent form (ICF) will be assigned a Subject ID number that will be entered on the eCRF. The Subject ID number will consist of 3 digits. Stratified randomization will be used to avoid bias in the assignment of subjects to treatment, to increase the likelihood that known and unknown subject attributes (e.g., demographics and baseline characteristics) are evenly balanced

across treatment groups, to reduce the possible influence of covariates on the drug evaluation, and to enhance the validity of statistical comparisons.

Subjects who satisfy all the entry criteria will be centrally assigned to study medication at the study site on Day 1 after stratification according to visual acuity (Baseline BCVA: ≤ 55 Letters versus > 55 Letters) and CST (screening CST: ≤ 450 μm versus > 450 μm) through the use of the IRT.

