8.3 Definition of Baseline

The baseline assessment will be the latest, valid pre-dose assessment available. Laboratory data may not be used from hemolyzed samples, mishandled samples, quantity not sufficient, or other conditions that would render the values invalid.

[figure not shown]

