13.1 Primary Analysis

The primary efficacy endpoint is change from baseline in BCVA letter count in the study eye at Week 16. Change from baseline in BCVA letter count will be calculated as Week 16 BCVA letter count minus Day 1 BCVA letter count such that a negative difference indicates a worsening in vision. In addition, treatment comparisons between each KVD001 Injection dose and the sham will be calculated as KVD001 Injection minus sham, such that a positive result indicates more letters gained in the KVD001 Injection treatment group. Treatment comparison between the KVD001 Injection doses will be calculated as KVD001 6 µg Injection minus KVD001 3 µg Injection, such that a positive result indicates more letters gained in the KVD001 6 µg Injection treatment group.

The study eye ETDRS letter scores including changes from baseline will be summarized using descriptive statistics for continuous variables. An analysis of covariance (ANCOVA) model will be used

to compare the change from baseline in BCVA letter count at Week 16 between each KVD001 Injection dose and the sham and between the KVD001 Injection doses.

Least-squares means (LSMeans) for each treatment group and its 95% CI will be presented. The LSMean difference between each KVD001 Injection dose and the sham and between the KVD001 Injection doses, their corresponding CIs, and the p-values will be presented.

[figure not shown]
Comparisons will use two-tailed, alpha=0.05 *t*-tests on the LSMean from the ANCOVA. LSMean for each treatment, the estimated treatment difference and the 95% CI for the difference will be calculated based on the ANCOVA model. An example of SAS® code implementation for changes from baseline in number of letters read correctly (using BCVA) is as follows:

[figure not shown]
```
proc mixed data=...;
  class ...;
  model ...;
  lsmeans ...;
run;
```

where

- | ...
- | ...
- | ...
- | ...

As a safeguard, the normality assumptions of the ANCOVA model used will be checked using a normal probability plot of the residuals and a plot of the residuals versus the fitted values (i.e., checking the normality assumption and the constant variance assumption of the model, respectively) to ensure that the model assumptions are reasonable. If there are any departures from the distributional assumptions, alternative methods of transformations may be explored.

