13.2 Additional Analyses of the Primary Endpoint

An analysis using observed data only will also be performed in both the FAS and PPS. Additionally, multiple imputation methodology will be used to impute missing data in the FAS for the analysis of the primary efficacy variables.

[Redacted text block]

[Redacted text block]

[Redacted text block]

- | [Redacted list item]
- | [Redacted list item]
- | [Redacted list item]
- | [Redacted list item]
- | [Redacted list item]
- | [Redacted list item]

[figure not shown]
[Redacted text block]

[Redacted text block]

[Redacted text block]

[Redacted text block]

- | [Redacted list item]

- [REDACTED]
- | [REDACTED]
- | [REDACTED]
- | [REDACTED]
- | [REDACTED]
- | [REDACTED]
- | [REDACTED]
- | [REDACTED]
- | [REDACTED]

As a sensitivity analysis, treatment group differences for changes from baseline in BCVA letter count will be evaluated using a mixed model repeated measures (MMRM) ANCOVA fitted with treatment group, visit and the treatment by visit interaction as categorical variable terms with baseline BCVA letter score and baseline CST as covariates with contrasts included for each visit. LSMeans and 95% CIs for each treatment group, the LSMeans difference between each KVD001 Injection dose and the sham and between the KVD001 Injection doses, the corresponding CIs, and the p-values will be presented for each visit. The covariance matrix will be attempted first with an unstructured covariance matrix, then with autoregressive 1 if the unstructured is not estimable.

Subgroup analyses of the primary endpoint for the study stratification factors will be presented.

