14.2.1.1.3	Analysis of Covariance of Change from Baseline in BCVA Letter Count in the Study Eye by CST Randomization Stratum and Visit	FAS Population ██████████
14.2.1.2	Analysis of Covariance of Change from Baseline in BCVA Letter Count in the Study Eye by Visit	FAS Population ██████████ ██████████
14.2.1.3.1	Analysis of Covariance of Change from Baseline in BCVA Letter Count in the Study Eye by Visit	FAS Population ██████ ██████████
14.2.1.3.2	Analysis of Covariance of Change from Baseline in BCVA Letter Count in the Study Eye by Visit	PPS Population ██████ ██████████
14.2.1.4	Mixed Model Repeated Measures Analysis of Covariance of Change from Baseline in BCVA Letter Count in the Study Eye by Visit	FAS Population ██████ ██████████
14.2.1.5.1	Proportion of Study Eyes with a ≥ 5 , ≥ 10 , and ≥ 15 BCVA Change from Baseline (Gain or Loss) by Visit	FAS Population ██████ ██████████
14.2.1.5.2	Proportion of Study Eyes with a ≥ 5 , ≥ 10 , and ≥ 15 BCVA Change from Baseline (Gain or Loss) by Visit	PPS Population ██████ ██████████
14.2.2.1	Analysis of Covariance of Change from Baseline in Central Subfield Thickness (μm) in the Study Eye by Visit	FAS Population ██████████
14.2.2.2	Analysis of Covariance of Change from Baseline in Central Subfield Thickness (μm) in the Study Eye by Visit	FAS Population ██████████ ██████████
14.2.2.3	Analysis of Covariance of Change from Baseline in Central Subfield Thickness (μm) in the Study Eye by Visit	FAS Population ██████ ██████████
14.2.2.4	Analysis of Covariance of Change from Baseline in Central Subfield Thickness (μm) in the Study Eye by Visit	PPS Population ██████ ██████████
14.2.2.5	Mixed Model Repeated Measures Analysis of Covariance of Change from Baseline in Central Subfield Thickness (μm) in the Study Eye by Visit	FAS Population ██████ ██████████
14.2.3.1	Proportion of Eyes with a ≥ 2 Step Improvement from Baseline in Diabetic Retinopathy Severity Scale Score by Visit	FAS Population ██████ ██████████
14.2.3.2	Proportion of Eyes with a ≥ 2 Step Improvement from Baseline in Diabetic Retinopathy Severity Scale Score by Visit	PPS Population ██████ ██████████
14.3.1.1.1	Overall Summary of Adverse Events (Ocular & Non-Ocular) by Treatment Group	SAF Population
14.3.1.1.2	Overall Summary of Adverse Events (Ocular) by Eye and Treatment Group	SAF Population
14.3.1.2.1	Treatment-Emergent Adverse Events by System Organ Class and Preferred Term	SAF Population

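### The protocol's primary ANCOVA leaves out CST, a stratification factor already used in the MMRM for the same endpoint; unless the redacted SAP model adds it, a small, nearly free precision gain goes unused

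*Protocol*

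**What the plan says.** Protocol Section 8 sets up the randomization: "Allocation to the treatments will be stratified by baseline BCVA" (55 letters or fewer against more) and by CST (450 µm or less against more). SAP Sections 4 and 4.1 repeat both factors; subjects are "centrally assigned to study medication at the study site on Day 1 after stratification according to visual acuity" and CST.

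For the primary endpoint, change in BCVA letters at Week 16, Protocol Section 8.5.1.2 and the synopsis give the model: "The ANCOVA model will include treatment as a main effect and baseline BCVA letter count as a covariate". CST is not in it. The next paragraph of Section 8.5.1.2 describes an MMRM sensitivity analysis of the same endpoint, and SAP Section 13.2 repeats it, with "baseline BCVA letter score and baseline CST as covariates with contrasts included for each visit".

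SAP Section 13.1 specifies an ANCOVA "to compare the change from baseline in BCVA letter count at Week 16 between each KVD001 Injection dose and the sham"; it also compares the two doses. Its readable text names no covariate, and the SAS model statement and legend are redacted. SAP Section 1 says: "The statistical analysis methods presented in this document will supersede the statistical analysis methods described in the clinical protocol". SAP Section 16, which lists changes from the protocol's analyses, mentions no change to the ANCOVA covariates.

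**The concern.** The sponsor treats CST as important enough to stratify on and to adjust for in the sensitivity model, yet the protocol leaves it out of the analysis that carries the conclusion. No reason is given.

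Stratifying on a prognostic variable makes the arms more alike, so the treatment difference varies less from trial to trial. A model without that variable does not credit this: its standard error still counts the CST-related variation as noise. The estimate is unbiased and type I error is not inflated, but the test falls below its nominal 5% and the interval is wider than it need be. If CST is unrelated to letter change, nothing is lost.

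There is also a cost in interpretation. When the primary ANCOVA and the MMRM have different covariates, a difference between them mixes the handling of missing data with the choice of covariates.

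**Working it through.** **Inputs.** From Protocol Section 8.8: 41 per arm, a 5-letter difference, pooled SD 7.5, two-sided α = 0.05. From Protocol Section 8: three arms, 1:1:1, four strata. The documents give no R² for CST. Here R² is the share of residual variance in letter change, after baseline BCVA, that CST explains; the assumed values are 0, 2%, 5% and 10%. The SD of 7.5 is taken as the residual SD after adjusting for baseline BCVA.

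**The plan's own figure.** A two-sample t-test with these inputs has 84.7% power (85.5% by normal approximation), against a stated figure of about 80%; 37 per arm would give 80.8%. An unstated dropout allowance of 10–12% would bring power to 80.7–79.7%. That gap is a separate matter and does not affect this point.

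**Base case, ANCOVA without CST.** SE = 7.5 × √(2/41) = 1.656. Error df = 123 − 4 = 119, critical value 1.980. The 95% CI half-width is 1.980 × 1.656 = 3.28 letters. Power with noncentrality 5/1.656 = 3.02 is 84.9%.

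**Type I error without CST.** Let b be the share of residual variance balanced by stratification. The true SE is √(1 − b) times the reported one, so type I error = 2 × P(T₁₁₉ > 1.980/√(1 − b)). If CST acts wholly through the 450 µm cut, b = R². If it acts linearly, with a normal distribution cut at its median, b = R² × 2/π. At R² = 10%:

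- via the cut: 1.980/√0.90 = 2.087, giving 3.90%
- linear: b = 0.0637, 1.980/√0.9363 = 2.046, giving 4.29%

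**Power with a CST term of the matching form.** SE = 1.656 × √(1 − R²), df 118. At R² = 10%: SE = 1.571, noncentrality 3.18, power 88.4%.

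| R² | Type I without CST (cut / linear) | Power without (cut / linear) | Power with matching term | Loss, points |
|---|---|---|---|---|
| 0 | 5.0% | 84.9% | 84.9% | 0 |
| 2% | 4.78% / 4.86% | 85.2% / 85.1% | 85.6% | about 0.5 |
| 5% | 4.44% / 4.64% | 85.6% / 85.3% | 86.7% | 1.1–1.4 |
| 10% | 3.90% / 4.29% | 86.2% / 85.7% | 88.4% | 2.2–2.7 |

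This closed form ignores chance imbalance in the added covariate. Multiplying the SE by √(1 + 1/117) to allow for it puts power at R² = 0 at 84.6%, a loss of 0.3 point, and the half-width at 3.29.

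**The term actually proposed: continuous baseline CST.** It fits a linear effect best and recovers less if the effect runs through the cut. Simulation: 20,000 trials per setting, 123 subjects, four strata, permuted blocks of 6 (assumed), correlation between the stratifying CST and the covariate CST of 1.0 or 0.9 (assumed). Power without → with CST, shown for correlation 1.0 / 0.9:

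| R² | Linear effect | Effect via the cut |
|---|---|---|
| 0 | 0.851→0.849 / 0.848→0.845 | same |
| 2% | 0.853→0.856 / 0.855→0.859 | 0.848→0.851 / 0.849→0.851 |
| 5% | 0.851→0.865 / 0.853→0.864 | 0.853→0.858 / 0.856→0.858 |
| 10% | 0.859→0.886 / 0.856→0.884 | 0.860→0.870 / 0.862→0.868 |

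Each simulated power has a Monte Carlo standard error of √(0.85 × 0.15/20,000) ≈ 0.0025, so differences of a few tenths of a point should not be over-read. With CST in the model, the half-width is about 3.29 letters at R² = 0, 3.25–3.27 at 2%, 3.20–3.25 at 5% and 3.11–3.20 at 10%. At R² = 10%, type I error moves from 4.4–4.6% to 5.1–5.2% (linear) and from 3.8–3.9% to 4.7–4.8% (via the cut).

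**The case against.** The strongest objection is that the governing text cannot be read. The SAP overrides the protocol, its model statement is redacted, and redacted content must not be treated as absent. The silence of SAP Section 16 is weak evidence, because that section also omits other visible changes: the 28-day limit on treatment-emergent events (Section 14.1), the categorical DRSS summary (Section 14.4) and the subgroup analyses by stratification factor (Section 13.2). This stands, and it is why the point is conditional.

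Second, a CST-adjusted Week 16 estimate is already planned through the MMRM, listed in SAP Section 19 as "Mixed Model Repeated Measures Analysis of Covariance of Change from Baseline in BCVA Letter Count in the Study Eye by Visit". That is true, but it is a sensitivity analysis and does not sharpen the primary one. The planned analyses by CST stratum do not replace covariate adjustment either.

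Third, the effect is small, rests on an assumed R², and errs on the conservative side in an exploratory Phase 2a trial whose calculated power is already near 85%. This also stands and limits the weight of the point.

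Fourth, the stratum is CST cut at 450 µm while the proposed term is continuous. If the effect runs only through the cut, the continuous term gains 0.2–0.5 of a 1.1-point loss at R² = 5%, and 0.6–1.0 of a 2.2-point loss at 10%. That is correct. The continuous term is still the natural choice because the MMRM already uses it. It also avoids a disagreement over when the stratifying CST is taken: Protocol Section 8 and SAP Section 4 say Screening, while Protocol Section 4.5.2 and SAP Section 3.1 say Day 1.

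**Conclusion.** The point holds as a low-weight suggestion about efficiency and consistency, conditional on SAP 13.1 having kept the protocol's covariates. The primary analysis is valid as the protocol states it.

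If CST explains 2–10% of the remaining variance, omitting it puts type I error at 3.9–4.9% instead of 5%, and the proposed term would gain roughly 0.2 to 2.8 points of power. If CST explains nothing, adding it costs about 0.3 point at most. These sizes depend on the assumed R², on 7.5 being the SD after BCVA adjustment, on a median cut for the linear case, and on the assumed block size and CST correlation.

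**What to change.** Confirm which covariates the redacted model in SAP 13.1 contains. If baseline CST is already there, only an entry in SAP Section 16 is needed.

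If it is not, add continuous baseline CST to the primary BCVA ANCOVA and to its by-visit, observed-data and multiple-imputation versions. Use the same variable as the MMRM and the baseline rule in SAP Section 8.3: "The baseline assessment will be the latest, valid pre-dose assessment available". Make the change before unmasking and list it in SAP Section 16.

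The cost is one model term and one degree of freedom. No new data are needed: SD-OCT is scheduled for every subject at Screening and Day 1.
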